6.5.3. Rescue Medicine

The study site will supply rescue medication that will be obtained locally. Rescue medication includes medications for the acute treatment of migraine. The following rescue medications may be used: triptans, ergotamines, NSAIDs, acetaminophen or combination analgesics (ie Excedrin[®]), opioids, or other medications that are not explicitly prohibited and may be taken during the study. In the Screening period, rescue medication can be taken if headache of any severity develops.

Although the use of rescue medications is allowable at any time during the study, the use of rescue medications should be delayed, if possible, for at least 2 hours following the administration of study intervention. The date and time of rescue medication administration as well as the name and dosage regimen of the rescue medication must be recorded.

6.5.4. Prohibited Interventions During the Study

Interventions that are prohibited during the entire study, including the duration of the Follow-up Visit, are described in [Table 6-2](#).

6.6. Dose Modification

No dose modification is allowed through the duration of the study

6.7. Intervention after the End of the Study

There will be no study intervention administered after the end of the study.

7. Discontinuation of Study Intervention and Participant Discontinuation/Withdrawal

A premature discontinuation will occur if a participant who signs the ICF and receives study intervention ceases participation in the study, regardless of circumstances, before the completion of the protocol-defined study procedures.

Notification of early participant discontinuation from the study and the reason for discontinuation will be made to the sponsor and will be clearly documented on the appropriate case report form.

Reasons for discontinuation from the study treatment and/or the study may include the following commonly used or other acceptable terms:

Commonly Used Terms	Other Acceptable Terms
Adverse event	Death
Lost to follow-up	Technical problems
Non-compliance with study drug	
Other	
Physician decision	
Pregnancy	
Protocol deviation	
Site terminated by sponsor	
Study terminated by sponsor	
Withdrawal by subject	

7.1. Discontinuation of Study Intervention

Criteria for discontinuation of the participant from study intervention are described above. Participants who discontinue study intervention must be discontinued from the study and should undergo EOD evaluations at early termination.

Discontinuation of study intervention due to any clinically significant findings in clinical laboratory determinations, vital sign or ECG measurements should be considered by the investigator if the investigator believes that it is in best interest of the participant. Any new clinically relevant finding should be reported as an AE.

Discontinuation of study intervention for abnormal liver function should be considered by the investigator when a participant meets one of the conditions outlined in Section 8.3.6 or if the investigator believes that it is in best interest of the participant.

See the SoA in Section 1.2 for data to be collected at the time of intervention discontinuation and follow-up and for any further evaluations that need to be completed.

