7.3. Lost to Follow Up

A participant will be considered lost to follow-up if he or she repeatedly fails to return for scheduled visits and is unable to be contacted by the study site.

The following actions must be taken if a participant fails to return to the clinic for a required study visit:

- The site must attempt to contact the participant and reschedule the missed visit as soon as possible and counsel the participant on the importance of maintaining the assigned visit schedule and ascertain whether the participant wishes to and/or should continue in the study.
- Before a participant is deemed lost to follow-up, the investigator or designee must make every effort to regain contact with the participant (where possible, 3 telephone calls, and if necessary, a certified letter to the participant's last known mailing address or local equivalent methods). These contact attempts will be documented in the participant's medical record.
- Should the participant continue to be unreachable, he/she will be considered to have withdrawn from the study.
- Discontinuation of specific sites or of the study as a whole are handled as part of [Appendix 1](#).

8. Study Assessments and Procedures

- Study procedures and their timing are summarized in the SoA. Protocol waivers or exemptions are not allowed.
- Immediate safety concerns should be discussed with the sponsor immediately upon occurrence or awareness to determine if the participant should continue or discontinue study intervention.
- Adherence to the study design requirements, including those specified in the SoA, is essential and required for study conduct.

- All screening evaluations must be completed and reviewed to confirm that potential participants meet all eligibility criteria. The investigator will maintain a screening log to record details of all participants screened and to confirm eligibility or record reasons for screening failure, as applicable.
- A detailed listing of study assessments by day is presented in [Appendix 8](#).

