8.3.6. AEs of Special Interest

AEs of special interest (AESI) that warrant ongoing monitoring and rapid communication by the investigator to the sponsor are potential Hy's Law cases and ALT/AST elevations, and are outlined below.

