8.3.6.2. ALT or AST Elevations

A treatment-emergent ALT or AST $\geq 3 \times$ ULN is considered an AESI. Any participant with this laboratory result after the study intervention was taken must have repeat testing within 48 to 72 hours to confirm the abnormality. For this repeat testing, the following labs must be drawn: hematology and chemistry panels, international normalized ratio (INR), serum acetaminophen level, urine drugs of abuse screen, and blood alcohol level. An extra blood serology sample must be collected and sent to the central laboratory for further diagnostic testing at a later date, if needed. In addition, the investigator will perform a complete history and examination to evaluate the participant for possible liver disease.

All AESIs must be reported to Allergan within 24 hours of the time the investigator becomes aware of the event using the abnormal liver function reporting form and the AE eCRF. All new elements of history, physical examination, diagnostic testing results, and other relevant medical reports are to be reported for each AESI.

If an ALT or AST elevation $\geq 3 \times$ the ULN is confirmed, close medical follow-up is required: For these participants, the following laboratory tests may be performed following consultation with the medical personnel at Allergan: anti-hepatitis A IgM, hepatitis B surface antigen, anti-hepatitis B core IgM, hepatitis C antibody, hepatitis C quantitative ribonucleic acid by polymerase chain reaction, anti-hepatitis E IgM, anti-hepatitis E IgG, Cytomegalovirus IgM antibody, and Epstein-Barr Virus IgM antibody. The participant must be followed clinically, and further medical evaluation (for other causes of acute hepatic injury) should be done per the judgment of the investigator and in conjunction with medical personnel at Allergan. In general, the chemistry panel should be repeated 1 to 2 times per week to follow the course of ALT/AST elevation.

Study interventions must be discontinued if any of the following criteria are met:

- ALT or AST $\geq 3 \times$ ULN and the participant is symptomatic with the appearance of fatigue, nausea, vomiting, right upper quadrant pain, or tenderness, fever, rash, or eosinophilia ($> 5\%$)
- ALT or AST $\geq 3 \times$ ULN and total bilirubin $> 2 \times$ ULN
- ALT or AST $\geq 3 \times$ ULN and INR > 1.5
- ALT or AST $\geq 5 \times$ ULN for more than 2 weeks
- ALT or AST $\geq 8 \times$ ULN

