The participant may be rechallenged with study intervention only after consultation with the Allergan Medical Monitor. For participants who are not rechallenged with study intervention, they should be discontinued from the study and complete an EOD Visit and Follow up Visit. Participants should receive appropriate follow-up as per standard of care.

The investigator must contact the Allergan Medical Monitor to discuss all cases of confirmed ALT/AST elevation $\geq 3 \times$ ULN. All ALT/AST elevations must be followed until ALT and AST return to $< 1.5 \times$ ULN and there is full clinical resolution.

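### Section 7.1 leaves optional a liver stop that Section 8.3.6.2 makes mandatory, and requires study exit where 8.3.6.2 allows rechallenge

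*Protocol*

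**What the plan says.** Section 7.1 of the protocol sets the general rule on leaving the study: "Participants who discontinue study intervention must be discontinued from the study and should undergo EOD evaluations at early termination". For abnormal liver function it says that stopping study intervention "should be considered by the investigator when a participant meets one of the conditions outlined in Section 8.3.6", or when the investigator thinks a stop serves the participant's interest.

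Section 8.3.6.2, which is part of 8.3.6, is firmer about the stop: "Study interventions must be discontinued if any of the following criteria are met". Five criteria follow:

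- ALT or AST at least 3 × ULN with listed symptoms or eosinophilia
- at least 3 × ULN with total bilirubin above 2 × ULN
- at least 3 × ULN with INR above 1.5
- at least 5 × ULN for more than 2 weeks
- at least 8 × ULN

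On what happens next, 8.3.6.2 is more permissive than 7.1: "The participant may be rechallenged with study intervention only after consultation with" the sponsor's Medical Monitor. Exit is then tied to the outcome of that decision: "For participants who are not rechallenged with study intervention, they should be discontinued from the study", with an EOD Visit and a Follow-up Visit.

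**The concern.** The two sections give the same participant different rules on two points.

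The first is the force of the stop. Section 7.1 treats every condition in 8.3.6 as a matter for judgement and does not set apart the five criteria at which 8.3.6.2 removes that judgement.

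The second is exit. Section 7.1 sends everyone who stops drug out of the study, which leaves no room for the rechallenge that 8.3.6.2 provides.

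This matters because potential Hy's law cases and ALT/AST elevations are the only adverse events of special interest named in Section 8.3.6, and 7.1 is the section whose title a site would look for when deciding whether to stop. Participant safety and consistent handling across up to 3 sites are at stake. The statistical analysis is not.

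**Working it through.** The plan gives no figure to reproduce here, so the check is a comparison of texts. The inputs are Sections 7.1, 8.3.6.1 and 8.3.6.2, and footnote a to Table 10-1 in Appendix 2.

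**Step 1. What the discretion in 7.1 covers.** It covers all of 8.3.6. Some of those conditions carry no mandated stop, for example an asymptomatic ALT or AST of 3 × ULN with bilirubin and INR not raised. For these, leaving the stop to judgement is right. The five criteria in 8.3.6.2 also lie within 8.3.6, and for them it is not. The overlap includes nearly all potential Hy's law cases. Section 8.3.6.1 asks for ALT or AST at least 3 × ULN and bilirubin at least 2 × ULN, and the second criterion in 8.3.6.2 requires a stop at the same transaminase level once bilirubin is above 2 × ULN.

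**Step 2. What a site can do when one of the five criteria is met.**

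| Action | Section 7.1 | Section 8.3.6.2 |
|---|---|---|
| Stop, no rechallenge, leave the study | complies | complies |
| Stop, consult the Medical Monitor, rechallenge, stay in the study | breaches the exit sentence | complies |
| Consider a stop, continue dosing | meets the wording of the liver sentence | breaches |

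One course satisfies both sections. The other two satisfy one section and breach the other.

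**Step 3. Which section prevails.** No text available to this review says. Footnote a to Table 10-1 describes 8.3.6 as the place for liver stopping criteria and required actions. That supports the mandatory reading and points to 7.1 as the section to correct.

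**Step 4. How far it can reach.** Ubrogepant is given on Day 1 and Days 12 to 15, and the antibody once on Day 8. For an elevation first seen after the Day 1 dose, the longest interval to the last dose is 15 − 1 = 14 days. That is not more than 2 weeks, so the 5 × ULN criterion could not withhold a dose. The other 5 − 1 = 4 criteria could. How many doses would be affected depends on when liver results become available. That schedule is in the SoA, which was not in the text supplied, so no dose count is offered. No event frequency can be derived from the documents either.

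**The case against.** The best defence is that the sections can be read together. Section 7.1 lists no liver criteria of its own and sends the reader to 8.3.6, where the mandatory wording heads the list. Its softer wording is correct for the conditions that carry no mandated stop. Rechallenge is an option, not a duty, and cannot happen without the Medical Monitor. Section 7 describes premature discontinuation as ceasing participation in the study, so stopping in 7.1 can naturally be read as stopping for good. A reader may also let the specific rule override the general one.

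There are further safeguards. Section 8 sends immediate safety concerns to the sponsor for a decision on whether to continue. Section 8.3.6.2 requires these events to be reported within 24 hours and the Medical Monitor to be contacted about every confirmed elevation of at least 3 × ULN.

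Most of this stands, and it keeps the point small. It does not remove the inconsistency, because the protocol states neither the permanent reading nor the precedence of 8.3.6.2, and sponsor contact does not settle which sentence governs.

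A reader might go further and infer that the two sections are opposites, so that obeying either one means departing from the other. The documents do not support that: the first row of the table complies with both. Nor do they show that dosing would in practice continue past a mandatory criterion. That would take a site that neither opened the section it was sent to nor acted on the required sponsor contact.

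**Conclusion.** The concern holds as an inconsistency of wording. Section 7.1 makes discretionary a stop that 8.3.6.2 makes mandatory at five criteria, and it requires exit for a participant whom 8.3.6.2 would allow to be rechallenged and kept.

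The severity is the lowest grade. The conflict takes effect only if a site doses on under 7.1 or rechallenges under 8.3.6.2. Events are expected to be rare, an expectation that rests on the statement in Section 2.2 that ubrogepant has shown no evidence of hepatotoxicity, not on any rate.

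A reader might also infer a threat to the drug-interaction result. There is none: the mixed model, the 90% confidence intervals and the 80% to 125% limits in protocol Section 9.4.1.2 and SAP Section 7.2 are the same whichever section is followed.

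The textual finding itself rests on no numerical assumption. It does assume that no part of the protocol missing from the supplied text says which section takes precedence.

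**What to change.** Make two edits to Section 7.1.

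1. Replace the liver sentence with wording such as: *Study intervention must be stopped when a participant meets any stopping criterion in Section 8.3.6.2. For any other condition in Section 8.3.6, or where the investigator judges a stop to be in the participant's interest, stopping should be considered.*
2. In the sentence on study exit, insert after its subject: *except those rechallenged under Section 8.3.6.2*.

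Section 8.3.6.2 can stay as it is. The cost is a wording change in one section, with the IRB approval that Section 10.1.1 requires for any amendment. There is no new visit, sample or analysis. The only discretion removed is at the five criteria, where 8.3.6.2 already withholds it.

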8.2.2. Vital Signs

Vital signs will be assessed as follows:

- Screening: Blood pressure (BP), pulse rate, respiratory rate, height, weight, and temperature
- Interim: BP and pulse rate

- EOD: BP, pulse rate, respiratory rate, weight, and temperature
- Blood pressure and pulse measurements will be assessed in a sitting position with a completely automated device. Manual techniques will be used only if an automated device is not available.
- Blood pressure and pulse measurements should be preceded by at least 5 minutes of rest for the participant in a quiet setting without distractions (eg, television, cell phones).
- Study center staff will assess vital signs at the nominal times (relative to the dosing time) or within 30 minutes prior to the nominal times (see Section 1.2, SoA, for additional details on assessment timepoints). Assessments performed outside this window will be noted as protocol deviations, and the reason for deviation must be documented in the source documents. Predose vital signs must be assessed within 120 minutes prior to the dosing time.
- For interim and EOD assessments, participants who have a sitting systolic BP ≥ 160 mm Hg or ≤ 90 mm Hg or who have a sitting diastolic BP ≥ 100 mm Hg or ≤ 45 mm Hg will undergo at least 2 BP reassessments within 15 minutes of the original. Participants who have a pulse rate > 100 bpm or < 45 bpm will undergo at least 2 pulse rate reassessments within 15 minutes of the original. If the second repeat of BP and/or pulse rate continues to be out of range, the investigator or subinvestigator must assess its clinical significance. Participants should be discontinued from the study if interim BP or pulse rate values are deemed clinically significant. If this occurs at screening, participants will be excluded from the study.

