8.2.3. Electrocardiograms

- A standard 12-lead ECG will be performed in the supine position at the nominal times (relative to the dosing times) or within 45 minutes prior to the nominal times as outlined in the SoA (see Section 1.2). Assessments performed outside this window will be noted as protocol deviations, and the reason for deviation must be documented in the source documents. Predose ECGs must be performed within 120 minutes prior to the dosing time.
- The paper speed will be a standard 25 mm/sec; the ECG tracing will be kept at the study center. Measurements will be recorded for the following parameters in lead II or lead III: heart rate, PR interval, QRS duration, QT interval, QTcB, and QTcF. All ECGs will be clinically interpreted by the investigator or subinvestigator.
- For interim and EOD ECGs, participants who have an abnormal QT result (QTcF ≥ 450 msec for male participants or ≥ 470 msec for female participants or uncorrected QT ≥ 500 msec) will undergo at least 2 ECG reassessments within 15 minutes of the original. If the second repeat of ECG results continues to be out of range, the investigator or subinvestigator must assess its clinical significance. Participants should be discontinued from the study if interim ECG results are deemed clinically significant.

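### Protocol Section 7.1 leaves stopping for abnormal liver tests to the investigator's discretion, while Section 8.3.6.2, to which it points, makes stopping mandatory on listed criteria

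*Protocol*

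**What the plan says.** Section 7.1 is the protocol's section on stopping study intervention. On liver tests it says "Discontinuation of study intervention for abnormal liver function should be considered by the investigator when a participant meets one of the conditions" given in Section 8.3.6, or if the investigator thinks stopping is in the participant's best interest. On other safety findings it says "Discontinuation of study intervention due to any clinically significant findings in clinical laboratory determinations, vital sign or ECG measurements should be considered", again subject to the investigator's view of the participant's best interest. It also ties stopping treatment to leaving the trial: "Participants who discontinue study intervention must be discontinued from the study".

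Section 8.3.6 covers the adverse events of special interest. Section 8.3.6.1 deals with potential Hy's Law cases and Section 8.3.6.2 with ALT or AST elevations. The latter contains the instruction "Study interventions must be discontinued if any of the following criteria are met", followed by five criteria.

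For interim vital signs, Section 8.2.2 says "Participants should be discontinued from the study if interim BP or pulse rate values are deemed clinically significant". Section 8.2.3 says "Participants should be discontinued from the study if interim ECG results are deemed clinically significant".

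Footnote a to Table 10-1 (Appendix 2) names Section 8.3.6 as the place where liver stopping criteria and required actions are found. The document supplied as the SAP is a PK data analysis plan. It defers safety analyses to a separate plan and says nothing about stopping rules.

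**The concern.** Section 7.1 refers to Section 8.3.6 as a whole and does not set apart the criteria that 8.3.6.2 makes mandatory. A site that starts from Section 7.1 finds only discretionary wording. Its opening sentence says the discontinuation criteria have already been described, but the text before it lists only the terms used to record a reason for stopping.

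Three things are at stake:

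- **Participant safety.** Potential Hy's Law cases and ALT/AST elevations are the only events of special interest in the protocol. A site could follow Section 7.1 and keep dosing a participant whom 8.3.6.2 says must stop.
- **Deviation handling.** Section 8 allows no waivers, and Section 10.1.9 sends significant deviations to the IRB. Continuing a participant who meets a listed criterion complies with 7.1 and breaches 8.3.6.2, so a monitor cannot classify the event consistently.
- **Data.** Adverse events leading to discontinuation are part of a secondary endpoint. PK1, the population for the primary comparison, needs evaluable ubrogepant parameters both alone and in combination, in parts of 20 participants each.

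**Working it through.** No sample size, error rate or model is involved, so the check is mainly a comparison of text, with one piece of date arithmetic.

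**1. Rules side by side**

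| Finding | Section 7.1 | Specific section | Result |
|---|---|---|---|
| One of the five listed ALT/AST criteria | Stopping to be considered | 8.3.6.2: stopping mandatory | Direct conflict |
| ALT or AST at least 3 x ULN, none of the five met | Stopping to be considered | 8.3.6.2: repeat testing, follow-up and reporting, no mandatory stop | No conflict |
| Interim BP or pulse rate judged clinically significant | Stopping to be considered, if in the participant's best interest | 8.2.2: should leave the study | Softer mismatch |
| Interim ECG judged clinically significant | Stopping to be considered, if in the participant's best interest | 8.2.3: should leave the study | Softer mismatch |

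A potential Hy's Law case under 8.3.6.1 carries reporting and evaluation duties there. It falls in the first row if it also meets the combined transaminase and bilirubin criterion of 8.3.6.2.

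**2. Does the difference between stopping treatment and leaving the study remove the mismatch?** Section 7.1 speaks of stopping study intervention; 8.2.2 and 8.2.3 speak of leaving the study. Because 7.1 itself requires anyone who stops intervention to leave the study, the two outcomes coincide and the mismatch stays.

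**3. Which liver criteria can affect dosing?** The first dose is on Day 1 and the last on Day 15 (Section 6.1). The longest time that a treatment-emergent elevation can have lasted by the last dose is 15 − 1 = 14 days. One criterion requires ALT or AST at least 5 x ULN for more than 2 weeks, that is, more than 14 days. Since 14 is not more than 14, no dose is left to withhold when it is met. That leaves 5 − 1 = 4 criteria for which the conflict can change dosing: the symptomatic, bilirubin, INR and 8 x ULN criteria.

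**4. When can a stop remove someone from PK1?** The comparison is Day 12 against Day 1 (Section 9.4.1.2; SAP Section 7.2). Sampling for the Day 12 profile ends 24 hours after that dose, on Day 13 (Section 8.5.1). A stop after that sample affects only the doses on Days 13, 14 and 15 and leaves PK1 unchanged. A stop before the Day 12 dose removes the participant, and one during the Day 12 profile may do so. The schedule of activities (Section 1.2) is not in the text available to me, so I cannot see which laboratory tests fall in that window.

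**5. How are the discontinuation events reported?** Section 9.4.2.1 provides a summary table of such events only if 5 or more participants have them, and a listing in any case. The effect on this endpoint component is therefore on a descriptive count.

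**The case against.** The strongest reply is that the passages form a general statement and a specific list. Section 7.1 sends the reader to 8.3.6, the Table 10-1 footnote does the same, and anyone who follows either pointer reaches the mandatory list. This stands only in part. I found no statement in the published text that the specific section prevails. Section 7.1 also attaches its discretionary wording to whatever is found in 8.3.6, so the cross-reference creates the clash instead of curing it.

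A second reply is that central controls limit divergence between the up to 3 sites. Section 8 sends immediate safety concerns to the sponsor to decide on continuing, events of special interest are reported within 24 hours, and the investigator must discuss every confirmed ALT/AST elevation of at least 3 x ULN with the sponsor's medical monitor. This stands as mitigation. It does not say which rule governs the decision.

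A third reply concerns vital signs and ECG. Neither side uses mandatory wording, and 8.2.2 and 8.2.3 come into play only after an investigator or subinvestigator has assessed values still out of range on the second repeat. This largely stands. What remains is that 7.1 adds a best-interest test that 8.2.2 and 8.2.3 do not contain.

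A reader might go further and infer that Section 7.1 contradicts every condition in 8.3.6, that all five listed criteria leave dosing in doubt, or that the vital-sign and ECG wording is as serious as the liver wording. The documents support none of these: elevations outside the list carry no mandatory stop, the 2-week criterion cannot act before the last dose, and the vital-sign and ECG passages differ only in strength of recommendation.

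**Conclusion.** The contradiction is real and should be fixed. For a participant who meets a listed criterion in Section 8.3.6.2, Section 7.1 permits what 8.3.6.2 forbids. It bears on dosing for four of the five criteria, assuming that the elevation is treatment-emergent and that dosing follows the planned days. The vital-sign and ECG mismatch is secondary.

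The main consequences are participant safety and inconsistent classification of deviations. It would be tempting to present this as a threat to the primary PK comparison, but the documents do not support that. Only stops before the Day 12 profile is complete can affect PK1, and Section 4.1 lets the sponsor replace participants who leave early. The number of participants affected cannot be derived from the documents and is probably small. I take no position on which stopping rule is right.

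**What to change.** Reconcile Section 7.1 with Section 8.3.6.2 so that one rule applies to each liver finding. Section 7.1 should separate the conditions in 8.3.6 that carry a mandatory stop from those that do not, and refer to 8.3.6.2 for the former, if the sponsor's medical team confirms that this is what is meant. Align the wording of 7.1 with 8.2.2 and 8.2.3 for interim blood pressure, pulse rate and ECG, and add cross-references to those sections. The choice of rule in each case is for the sponsor's medical team.

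The same edit should check one neighbouring sentence. Section 8.3.6.2 allows for rechallenge after consultation with the medical monitor, while Section 7.1 requires everyone who stops intervention to leave the study. These also need to be reconciled.

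The cost is a wording change in a protocol amendment or clarification letter. Sample size, assessments and the PK analysis need no change.
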